# **Study Procedures**

#### Suicidal Ideation and Behavior

Does this research qualify as a clinical investigation that will utilize a test article (ie-drug or biological) which may carry a potential for central nervous system (CNS) effect(s)? No

#### **Procedures**

Patients presenting to the Department of Endodontics, School of Dental Medicine, University of Pennsylvania for evaluation and routine endodontic treatment of infected, necrotic teeth with chronic apical periodontitis will be asked to take part in the study if they meet the inclusion criteria specified below and volunteer to participate. Prior to patient recruitment a randomized chart was drafted that assigns teeth to either NaOCL, saline or Feraheme/H2O2 (amended). After eligibility of the patient is confirmed, the randomly assigned protocol for the tooth to be treated will be looked up by the principal investigator. Before treatment, patients will be thoroughly informed about the nature, potential risks and alternatives of the study as well as the root canal treatment. Patients will be presented with a written consent form regarding the above mentioned study characteristics (amended to this IRB proposal) as well as the regular consent forms for the root canal therapy, including the consent form for endodontic treatement, acknowledgement of privacy practices and a patient understanding and informed consent form. Patients will be eligible to participate in the study for NaOCL (positive control), saline (negative control or Feraheme/H2O2 if the following inclusion criteria are met: 1. Patients to welling to participate in the study. 2. Patients are 18 years or above. 3. Non-contributory medical history (Patient can be seen for regular dental appointment in PDM; ASA classes I and II). 4. Tooth requiring root canal treatment with radiographic presence of periapical radiolucency and responding to thermal sensitivity testing negatively


#### The following documents are currently attached to this item:

 ${\it There \ are \ no \ documents \ attached for \ this \ item.}$ 

# Deception

Does your project use deception? No

#### **Analysis Plan**

After incubation the number of colony forming units will be determined by using a stereoscope. ANOVA and Students t-test will be used for statistical analysis.

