# Primary outcome variable(s)

Studies has shown that the bacteria within tooth root canal system is the primary etiology for the root- end disease process. The reduction or elimination of microorganisms from the root canal system of infected teeth has been shown to correlate with the long-term success of the endodontic treatment. The main objective of root canal treatment is to disinfect root canal systems entirely and seal to prevent further contamination. However, with current techniques, it is impossible to eradicate bacteria and biofilm completely from the complex root canal system. This study is designed to evaluate the antibacterial efficacy of Feraheme/H2O2 and to compare it to the routinely used protocol. The outcome

will be evaluated by taking bacterial samples from the root canals during routine root canal treatment after applying different disinfection protocols. Bacteria from each sample will be quantified. The primary outcome parameter will be the difference in bacterial reduction between the experimental group (Feraheme) and a comparison group (routinely used protocol).

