# Secondary outcome variable(s)

Complex anatomy limit the efficacy of disinfection solutions and protocols. By evaluating bacterial reduction in different canal configurations, we will have a better understanding on the efficacy of tested solutions. Furthermore, proof-of-concept experiments in endodontic treatment could open the door for Feraheme to be used in numerous clinical anti-biofilm applications.

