#### Design

Patients presenting to the Department of Endodontics, School of Dental Medicine, University of Pennsylvania for evaluation and routine endodontic treatment of infected, necrotic teeth with chronic apical periodontitis will be asked to take part in the study if they meet the inclusion criteria specified below and volunteer to participate. Prior to patient recruitment a randomized chart was drafted that assigns teeth to either NaOCL or Feraheme/H2O2 (amended). After eligibility of the patient is confirmed, the randomly assigned protocol for the tooth to be treated will be looked up by the principal

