#### **Subject Confidentiality**

Patients will be presented with a written consent form regarding the above mentioned study characteristics (research consent form, amended to this IRB proposal) as well as the regular consent forms for the root canal therapy, including the consent form for endodontic treatement, acknowledgement of privacy practices and a patient understanding and informed consent form. Patients signed consent forms will collected and stored by the PI in a secure, restricted area. Study data will be stored on an institutionally secured and managed device or server. The information collected and used for research purposes will be the School of Dental School Medicine chart number, diagnosis and tooth number. No protected health information such as name, address, telephone number, date of birth, social security number, personal and family medical history or results from physical examinations, tests or procedures will be used or collected. The chart number will only be recorded for a possible future verification of the research data such as tooth number and diagnosis. Patients chart number is secured by a login and password only accessible to students, residents and faculty of the dental school. Diagnosis and tooth number will be used in this investigation for scientific publication or presentation at scientific meetings.

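### The primary comparison is planned without adjustment for tooth type or the baseline count, both available; the test stays valid, but precision may be lost and a chance imbalance would stand uncorrected

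*Combined protocol and SAP*

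**What the plan says.** - **Analysis.** The Analysis Plan says that "ANOVA and Students t-test will be used for statistical analysis". Design and Procedures repeat this and add no covariate, second factor or stratum.
- **Primary outcome.** Under Primary outcome variable(s): "The primary outcome parameter will be the difference in bacterial reduction between the experimental group (Feraheme) and a comparison group (routinely used protocol"). Procedures takes sample S1 before and S2 after the test irrigant, so the outcome is a change within the tooth.
- **Allocation.** Procedures states that "a randomized chart was drafted that assigns teeth to either NaOCL, saline or Feraheme/H2O2". Design describes the same chart with NaOCl and Feraheme/H2O2 only. Neither section mentions strata, blocks or a ratio, and the chart is not reproduced.
- **Anatomy.** Secondary outcome variable(s) states: "Complex anatomy limit the efficacy of disinfection solutions and protocols". It then announces an evaluation by canal type ("By evaluating bacterial reduction in different canal configurations") but gives no method.
- **Entry.** Key inclusion criteria admit single-canal teeth and also single-canal roots of multirooted teeth. Under Procedures, a tooth whose configuration is not confirmed at access is left out.
- **Data held.** The research items listed under Subject Confidentiality are "chart number, diagnosis and tooth number". Tooth number also goes on every sample vial.
- **Size.** Study duration gives 60 teeth. Accrual offers no power calculation.

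**The concern.** The plan names anatomy as something that limits how well an irrigant works and holds a pre-treatment item related to it, but the primary comparison does not use that item. Two things follow. Any variation between teeth that tooth type explains stays in the error term, which costs precision in a study of only 60 teeth. And if one arm happens to receive more roots of multirooted teeth, the planned tests do nothing to separate that difference from the irrigant effect in the one result the trial will report.

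The same applies to S1, the baseline count. It is collected for every tooth and used to form the reduction, but it is not named as a covariate.

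**Working it through.** **Inputs from the documents.** 60 teeth in total. With equal allocation (assumed, as no ratio is given) this is 60/3 = 20 per arm under the three-arm text or 60/2 = 30 under the two-arm text. The 60 cannot be reproduced, because no alpha, power, effect size or SD is stated.

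**Assumptions.** Two-sided alpha 0.05; tooth type as a two-level factor, half the teeth in each class; R2, the share of outcome variance that tooth type explains, from 0 to 0.30. The documents give none of these.

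**1. How often imbalance arises.** Under simple randomisation the number of multirooted teeth in each arm is Binomial(n, 0.5). A 20-point gap is at least 4 teeth at n = 20 or 6 teeth at n = 30. Summing the exact probabilities gives 0.268 (n = 20) and 0.155 (n = 30). If arm sizes and the overall mix are held fixed (hypergeometric, 30% or 50% in one class), the figures are 0.30 to 0.34 and 0.16 to 0.20.

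**2. What such a gap does.** With an even mix, the tooth-type effect in total SD units is sqrt(R2/0.25) = 2·sqrt(R2). A 20-point gap shifts the unadjusted difference by 0.20 × 2·sqrt(R2):

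| R2 | Tooth-type effect | Shift |
|---|---|---|
| 0.05 | 0.45 SD | 0.09 SD |
| 0.10 | 0.63 SD | 0.13 SD |
| 0.20 | 0.89 SD | 0.18 SD |
| 0.30 | 1.10 SD | 0.22 SD |

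For scale, the difference detectable with 80% power is 0.91 SD at 20 per arm and 0.74 SD at 30.

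**3. Validity.** In simulations (8,000 runs per setting, R2 0.10 and 0.30) the unadjusted t-test after unstratified allocation kept its type I error at 0.048 to 0.053.

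**4. Power.** Adjustment multiplies the error SD by sqrt(1 − R2), so a difference d acts as d/sqrt(1 − R2). Two-sample noncentral t on the two arms compared, noncentrality d·sqrt(n/2)/sqrt(1 − R2), one degree of freedom lost, d = 0.8 SD (chosen for illustration):

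| | 20 per arm | 30 per arm |
|---|---|---|
| Unadjusted | 69.3% | 86.1% |
| Adjusted, R2 = 0 | 69.3% | 86.1% |
| R2 = 0.05 | 71.5% | 87.8% |
| R2 = 0.10 | 73.8% | 89.4% |
| R2 = 0.20 | 78.7% | 92.6% |
| R2 = 0.30 | 83.8% | 95.4% |

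Starting instead from exactly 80% unadjusted power, adjustment gives about 82%, 84%, 88% and 92% at R2 0.05, 0.10, 0.20 and 0.30 for either arm size. A second lost degree of freedom, for S1, lowers each adjusted figure by less than 0.1 point. The gain from S1 itself cannot be sized, because the documents give no correlation between S1 and the reduction.

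**5. Stratifying without adjusting.** Stratification shrinks the true variance of the difference by the factor 1 − R2, but the plain t-test still uses the full variance. Its type I error is then about P(|Z| > 1.96/sqrt(1 − R2)): 1.96/0.949 = 2.07 gives 0.04 at R2 0.10, and 1.96/0.837 = 2.34 gives 0.02 at R2 0.30. Simulation agrees (0.038 to 0.041 and 0.020 to 0.021). Stratifying and adjusting restores 0.050 to 0.052.

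**The case against.** A reader might infer that the plan ignores anatomy. It does not. Sampling is limited to single canals, unconfirmed configurations are left out, and a secondary outcome looks at canal configuration. That stands. What is missing is a method for that secondary look and any link from it to the primary comparison.

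It can also be said that tooth type is not the factor the plan names. The plan speaks of canal configuration, and the Background lists isthmuses, ramifications, accessory canals and dentinal tubules. Nothing in the documents shows that single-rooted against multirooted predicts disinfection once only single canals are sampled, or that tooth number alone settles root class. This also stands: tooth type is a plausible proxy, not an established source of variance. An R2 of 0.20 or 0.30 would need a tooth-type effect of 0.89 or 1.10 SD, larger than the 0.8 SD irrigant effect used in the illustration, so the upper rows of the power table should not be relied on.

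Third, the outcome is already a within-tooth reduction, which takes account of part of the difference in starting load. That is true in part. Subtracting a baseline is not the same as adjusting for it, and S1 is the more obvious covariate.

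What the objections do not remove is that entry still mixes two tooth classes and that prespecified adjustment costs almost nothing if the factor proves irrelevant.

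**Conclusion.** The point holds as a low-cost gain in precision and protection against chance imbalance. The primary comparison is unadjusted as written, and no stratification is described. An imbalance of 20 points or more is plausible (about 27% of trials at 20 per arm, 15% at 30, assuming simple randomisation and an even mix), and the named tests would not correct it. The likely gain from adjusting for tooth type is about 2 to 4 power points at R2 0.05 to 0.10 and nil at R2 0. It is larger only if tooth type matters more than the documents show, and the single-canal restriction may keep it small.

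Three stronger readings are not supported:
- Chance imbalance does not make the test invalid or raise its type I error.
- A loss of power is not demonstrated, since the documents give no variance, tooth mix or tooth-type effect.
- The chart cannot be called unstratified, because it is not shown. One can say only that no strata are described.

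**What to change.** 1. In the Analysis Plan, prespecify the primary model as a linear model for bacterial reduction with treatment, tooth type (single-rooted against root of a multirooted tooth) and the baseline S1 count, on the same scale as the outcome. Derive tooth type from the recorded tooth number, and from the pre-treatment radiograph where the number is ambiguous.
2. Reconcile the two-arm text in Design with the three-arm text in Procedures. Arm size and any redrawn chart depend on it.
3. After that, and only for teeth not yet allocated, stratify the chart by tooth type. If this is done, the adjusted model is primary, and any unadjusted comparison reported beside it is labelled as conservative.
4. State in the plan how the existing chart was generated. If it was already stratified, the factor belongs in the model for the reason shown in step 5 of the working.

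The cost is a few lines of text and about two degrees of freedom. No new sample or examination is needed. Where the radiograph decides, root class is noted from an image already required for entry. The model change can be made even if allocation is complete, provided it is fixed before results are compared by arm.

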#### The following documents are currently attached to this item:

There are no documents attached for this item.

Are you conducting research outside of the United States? No

# Data confidentiality

- ${\bf x}$  Paper-based records will be kept in a secure location and only be accessible to personnel involved in the study.
- x Computer-based files will only be made available to personnel involved in the study through the use of access privileges and passwords.
  - Prior to access to any study-related information, personnel will be required to sign statements agreeing to protect the security and confidentiality of identifiable information.
- x Wherever feasible, identifiers will be removed from study-related information.
  - A Certificate of Confidentiality will be obtained, because the research could place the subject at risk of criminal or civil liability or cause damage to the subject's financial standing, employability, or liability.
  - A waiver of documentation of consent is being requested, because the only link between the subject and the study would be the consent document and the primary risk is a breach of confidentiality. (This is not an option for FDA-regulated research.)
  - Precautions are in place to ensure the data is secure by using passwords and encryption, because the research involves web-based surveys.
  - Audio and/or video recordings will be transcribed and then destroyed to eliminate audible identification of subjects.

#### **Subject Confidentiality**

Patients will be presented with a written consent form regarding the above mentioned study characteristics (research consent form, amended to this IRB proposal) as well as the regular consent forms for the root canal therapy, including the consent form for endodontic treatement, acknowledgement of privacy practices and a patient understanding and informed consent form. Patients signed consent forms will collected and stored by the PI in a secure, restricted area. Study data will be stored on an institutionally secured and managed device or server. The information collected and used for research purposes will be the School of Dental School Medicine chart number, diagnosis and tooth number. No protected health information such as name, address, telephone number, date of birth, social security number, personal and family medical history or results from physical examinations, tests or procedures will be used or collected. The chart number will only be recorded for a possible future verification of the research data such as tooth number and diagnosis. Patients chart number is secured by a login and password only accessible to students, residents and faculty of the dental school. Diagnosis and tooth number will be used in this investigation for scientific publication or presentation at scientific meetings.

#### **Sensitive Research Information\***

Does this research involve collection of sensitive information about the subjects that should be excluded from the electronic medical record?

No

# **Subject Privacy**

Privacy refers to the person's desire to control access of others to themselves. Privacy concerns people, whereas confidentiality concerns data. Describe the strategies to protect privacy giving consideration to the following: The degree to which privacy can be expected in the proposed research and the safeguards that will be put into place to respect those boundaries. The methods used to identify and contact

potential participants. The settings in which an individual will be interacting with an investigator. The privacy guidelines developed by relevant professions, professional associations and scholarly disciplines (e.g., psychiatry, genetic counseling, oral history, anthropology, psychology).

Patients signed consent forms will collected and stored by the PI in a secure, restricted area. The information collected and used for research purposes will be the School of Dental School Medicine chart number, diagnosis and tooth number. No protected health information such as name, address, telephone number, date of birth, social security number, personal and family medical history or results from physical examinations, tests or procedures will be used or collected. The chart number will only be recorded for a possible future verification of the research data such as tooth number and diagnosis. Patients chart number is secured by a login and password only accessible to students, residents and faculty of the dental school. Treatments will be done at the University of Pennsylvania School of Dental Medicine Endoodontic clinic. All root canal procedures within the Dental School is done in the Endodontic clinic where work stations are designed to accommodate patient's privacy. Endodontic clinic contains a separate private room in cases where research instructions or patient's concerns can be addressed.

#### **Data Disclosure**

Will the data be disclosed to anyone who is not listed under Personnel? The data will not be disclosed to anybody who is not listed under Personnel.

#### Data Protection\*

Name

Street address, city, county, precinct, zip code, and equivalent geocodes

All elements of dates (except year) for dates directly related to an individual and all ages over 89

Telephone and fax number

Electronic mail addresses

Social security numbers

Medical record numbers

Health plan ID numbers

**Account numbers** 

Certificate/license numbers

Vehicle identifiers and serial numbers, including license plate numbers

Device identifiers/serial numbers

Web addresses (URLs)

**Internet IP addresses** 

Biometric identifiers, incl. finger and voice prints

Full face photographic images and any comparable images

x Any other unique identifying number, characteristic, or code

None

Does your research request both a waiver of HIPAA authorization for collection of patient information and involve providing Protected Health Information ("PHI") that is classified as a "limited data set" (city/town/state/zip code, dates except year, ages less than 90 or aggregate report for over 90) to a recipient outside of the University of Pennsylvania covered entity?

# Tissue Specimens Obtained as Part of Research\*

Are Tissue Specimens being obtained for research? No

#### Tissue Specimens - Collected during regular care\*

Will tissue specimens be collected during regulator clinical care (for treatment or diagnosis)?

#### Tissue Specimens - otherwise discarded\*

Would specimens otherwise be discarded?

No

# Tissue Specimens - publicly available\*

Will tissue specimens be publicly available?

No

#### Tissue Specimens - Collected as part of research protocol\*

Will tissue specimens be collected as part of the research protocol?

No

# Tissue Specimens - Banking of blood, tissue etc. for future use\*

Does research involve banking of blood, tissue, etc. for future use?

No

#### Genetic testing

If genetic testing is involved, describe the nature of the tests, including if the testing is predicative or exploratory in nature. If predictive, please describe plan for disclosing results to subjects and provision of genetic counseling. Describe how subject confidentiality will be protected Note: If no genetic testing is to be obtained, write: "Not applicable."

Not applicable

# Consent

# 1. Consent Process

#### Overview

Patients routinely sign a consent form before being seen in the endodontic clinic. This form reviews the routine root canal procedure and any risks associated with it. We review routinely the consent form and health history with the patient and answer any questions that they may have on root canal procedures. The language used in the consent form is meant for lay-people and is not scientific in nature. If a patient chooses to participate in our study, they will sign an additional consent form for participation prior to participating. They will be made aware that if they do not wish to participate, they will not receive any treatment that is subpar as opposed to if they did agree to participate. The examiners will review the consent form with the patient and answer any questions they may have. If at any point, a patient decides they no longer want to participate, they will be excused from the study and will continue treatment as needed.

#### Children and Adolescents

N/A

#### **Adult Subjects Not Competent to Give Consent**

N/A

# 2. Waiver of Consent

# Waiver or Alteration of Informed Consent\*

No Waiver Requested

Minimal Risk\*

Impact on Subject Rights and Welfare\*

Waiver Essential to Research\*

**Additional Information to Subjects** 

Written Statement of Research\*

No

If no written statement will be provided, please provide justificiation

The following documents are currently attached to this item:

There are no documents attached for this item.

# Risk / Benefit

# **Potential Study Risks**

Only the risks or discomforts that can arise during or after any routine root canal treatment procedure apply. Bacterial sampling will not have any adverse effect on the treatment or on treatment outcome. There are no potential risks expected from the noninvasive bacteriological sampling, including any potential physical, psychological, social, economic, monetary, legal or other risks. Identifying the antibacterial benefits of Feraheme/H2O2 irrigation is the goal of our experiment. Feraheme with much higher concentrations has been used in medicine as IV to improve and heal patients iron deficiency. Feraheme used in this experiment is limited within the root canal system and applied on dentine surfaces only. It will not be used systemically. Solution will be kept within the root canal system for a couple of minutes proposed in this protocol and will be evacuated by sterile saline, dental suction and paper points. Experiment was designed that the final root canal disinfection is not relying on experimental solutions antibacterial effect only. After bacterial sampling, antibacterial medication (CaOH2) will placed as done routinely to treat cases with pulp necrosis and apical periodontitis. Besides tooth number, diagnosis and the PDM chart number (for potential verification of study correctness) no patient data will be collected by the PI. All treatment procedures at the PDM, including the routine root canal treatment of the participants, during which the samples will be taken, are subject to strict HIPPA (privacy) and OSHA (hygiene) regulations.

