
endodontic applications, only a single topical treatment of up to 6 mg (which is 85 times less than the FDA-approved dose) would be used for a transient exposure (for less than 10 minutes) of infected tooth canal in the oral cavity, supporting the potential clinical translation of a Feraheme/H2O2 anti-biofilm treatment. Proof-of-concept experiments in endodontic treatment could open the door for Feraheme to be used in numerous clinical anti-biofilm applications. The assessment of bacterial reduction during endodontic therapy by bacterial sampling and culturing is an established technique and has been used to evaluate treatment protocols or variations thereof (15-18). There is a current need for a better disinfecting agent that is capable of overcoming the limitations of the currently used irrigation solutions, and based on our preliminary findings, CAT-NP/H2O2 has a potential as a novel anti-biofilm clinical therapy with its potent antibacterial and anti-biofilm activities. The purpose of this study is to develop an irrigation disinfection protocol for eradicating biofilms with a clinically approved and commercially available iron oxide nanoparticle formulation Feraheme. This protocol will be testing local application of Feraheme within the canal system in patients going through routine endodontic treatment, will evaluate its potential as a novel anti-biofilm disinfection solution and compare it to other currently used antibacterial protocols.

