#### **Data and Safety Monitoring**

Investigators listed on the proposal will monitor the progress of the experiment. Routine meetings will be conducted to assess the number of samples collected, results, patient comments and complains, investigators' comments and findings.

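### The risk section says only routine root canal risks apply, although two exclusions are specific to the study drug, and no supplied section provides for recording reactions by arm

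*Combined protocol and SAP*

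**What the plan says.** **Risk statement.** Potential Study Risks opens with: "Only the risks or discomforts that can arise during or after any routine root canal treatment procedure apply". On exposure it says: "Solution will be kept within the root canal system for a couple of minutes proposed in this protocol", after which the solution is removed with saline, suction and paper points. Risk / Benefit Assessment likewise expects no risks from the experiment, and its text then breaks off.

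**Eligibility.** Key exclusion criteria, repeated under Design and Procedures, excludes known hypersensitivity to ferumoxytol or any iron product (exclusion 4) and a head MRI scheduled within three months after the nanoparticles are applied (exclusion 5). Exclusion 3 removes patients with multiple drug allergies. Drugs or Devices records use outside the approved labelling, and IND Exemption is marked as obtained.

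**Data and monitoring.** Potential Study Risks says: "Besides tooth number, diagnosis and the PDM chart number (for potential verification of study correctness) no patient data will be collected by the PI". Subject Confidentiality agrees: "The information collected and used for research purposes will be the School of Dental School Medicine chart number, diagnosis and tooth number". Data and Safety Monitoring provides this: "Routine meetings will be conducted to assess the number of samples collected, results, patient comments and complains, investigators' comments and findings". The Analysis Plan covers colony counts only.

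**The concern.** There are two linked problems.

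First, the risk statement is absolute, but the plan acts on two matters that routine root canal therapy does not raise. A patient is kept out for iron or ferumoxytol hypersensitivity, or for a forthcoming head MRI, only because of the study drug. The exclusions can remove a known hypersensitivity or a scan already scheduled. They cannot remove a first reaction or a scan that becomes necessary later.

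Second, the risk section states a short list of patient data, and reactions are not on it. Meetings may discuss a complaint, but no supplied section names an event definition, a form, a time window or a count by arm. A team that followed the text would finish with colony counts and no systematic tolerability record. The protocol hopes that Feraheme will go on to other anti-biofilm uses, and later work would want a simple count of how many patients in each arm had a reaction.

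**Working it through.** **1. The plan's own exposure figure.** Background gives an intravenous dose of 510 mg and a topical dose of up to 6 mg. 510 / 6 = 85, which reproduces the stated 85-fold difference. The low dose is therefore correctly described and counts in the plan's favour.

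**2. Risk statement against eligibility.**

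| Item | Part of routine root canal risk? | Acted on in the plan? | Named in Potential Study Risks? |
|---|---|---|---|
| Ferumoxytol or iron hypersensitivity | No | Yes, exclusion 4 | No |
| Head MRI within three months after application | No | Yes, exclusion 5 | No |

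The plan gives no reason for the MRI criterion, so the documents cannot show whether it concerns harm or image quality. In either case it is a restriction that comes with the drug.

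**3. Contact time.** Design and Procedures give one 2 mL introduction and a further 2 mL after each of three files: 2 + 3 × 2 = 8 mL, with a total contact time of 10 minutes. Over four introductions, if evenly split (an assumption), this is 10 / 4 = 2.5 minutes each. The risk section's phrase fits one introduction. It does not give the total.

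**4. What a reaction count could show.** Inputs: 60 teeth (Accrual, Study duration). Procedures lists three arms and Design's randomisation sentence lists two. Assuming equal allocation, the Feraheme arm has 60 / 3 = 20 or 60 / 2 = 30 teeth. Assuming also one tooth per patient, n = 20 or 30 patients.

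With zero events, the one-sided 95% upper limit is 1 − 0.05^(1/n):
- n = 20: 1 − 0.05^(1/20) = 13.9%
- n = 30: 1 − 0.05^(1/30) = 9.5%

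The chance of at least one event at true rate p is 1 − (1 − p)^n:

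| True rate (assumed) | n = 20 | n = 30 |
|---|---|---|
| 1% | 18% | 26% |
| 5% | 64% | 79% |
| 10% | 88% | 96% |

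A count would probably reveal common reactions and would usually miss rare ones.

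**5. The unit.** Allocation is by tooth, and the plan does not say that each patient contributes one tooth. Hypersensitivity occurs in a patient. If some patients contribute two teeth there are fewer patients than teeth and the limits widen. If the two teeth are in different arms, a systemic reaction belongs to no single arm.

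**The case against.** The best defence is that the exposure is trivial and already guarded: at most 6 mg, confined to the canal and washed out, with known hypersensitivity and multiple drug allergies excluded. The section adds: "Experiment was designed that the final root canal disinfection is not relying on experimental solutions antibacterial effect only". Much of this stands, and it justifies calling the risk low. The last sentence, however, answers a worry about inadequate disinfection, not one about a reaction to the drug. None of it supports a statement that nothing beyond routine risk applies.

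Four stronger readings are tempting, and the documents do not support them.

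- *Contact time is understated several-fold.* This requires the risk section to be describing the total. It may describe a single introduction, and it refers back to the protocol. Design and Procedures agree on 10 minutes, so no operator is misled. The Background wording, "would be used for a transient exposure (for less than 10 minutes) of infected tooth canal", differs trivially from 10 minutes.
- *The plan forbids a reaction count.* The sentence in Subject Confidentiality and Subject Privacy that ends "personal and family medical history or results from physical examinations, tests or procedures will be used or collected" is a negative statement about protected health information. It does not clearly bar a de-identified count. The list of patient data is also not literally complete, because vial labels carry the experimental group and colonies are counted. Since each tooth's assignment is known, a later tabulation is not precluded; it is just not provided for.
- *Safety is unmonitored.* Meetings do review patient complaints and investigators' findings, and Resources necessary for human research protection covers medical needs during treatment.
- *Patients are not told of drug risks.* The consent form and the FDA document listed under General Attachments were not supplied, and Risk / Benefit Assessment stops where it may have described the handling of problems. Nothing can be said about them.

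**Conclusion.** The point holds at a low level, as something to consider. The word only in the risk section does not fit the plan's own drug-specific exclusions for a product used outside its labelling. The section's stated limit on patient data, together with monitoring by meeting, means that the supplied text does not provide for recording reactions by arm. The second finding is limited to that text.

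The documents do not show that topical Feraheme is hazardous, and the exclusions are not evidence that it is. The bacterial-reduction comparison is unaffected. The statistical gain is modest: an upper limit of 13.9% or 9.5% after zero events, under the assumptions of equal allocation and one tooth per patient.

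**What to change.** 1. In Potential Study Risks, replace the absolute statement with one that says the added risk is expected to be low, names possible hypersensitivity and the head-MRI restriction, and gives the 10-minute total contact time from Design and Procedures.
2. Record reactions and symptoms for every patient in every arm on one short form at the treatment visit and at the existing one-to-four-week return visit.
3. Amend the data-collection sentence in Potential Study Risks to allow this, and Subject Confidentiality and Subject Privacy if needed.
4. Tabulate descriptively as x of n patients by arm, without a test. State in advance how a patient with teeth in more than one arm is counted.

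By the return visit all arms have also received 3% NaOCl and calcium hydroxide, so symptoms reported then reflect the whole treatment sequence and should be labelled as such.

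The cost is one form at two visits that already take place, a few reworded sentences, and a small amendment, including the consent or HIPAA wording where required. The downsides are slightly more patient data, a somewhat less favourable risk statement, and a table that can show only common reactions.
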